11.5.6. Echocardiography Measurement

If an echocardiography was performed by the standard of care since last visit, collect the subject's most recently obtained echo values and the date of measurement.

- LVEF
- LVESV
- LVEDV
- Aortic VTI
- Mitral Valve Regurgitation

11.5.7. Current Device Settings and Status

Print a copy of the Quick Notes Report from the PRM to document current device settings and status prior to conducting any test and changing the programming settings. A list of settings and status, including but not limited to the SmartDelay settings, percent of pacing (%RA paced, % RV paced, %LV paced), and percent of AT/AF (%AT/AF) are required to be collected.

11.5.8. Lead Measurements

The following lead measurements are required to be collected for the RA lead, RV lead, and LV lead:

- Intrinsic amplitude (mV)
- Pacing capture threshold (PCT in V; the recommended pulse width is 0.4 ms)
- Pacing lead impedance (Ω)
- Shocking lead impedance (Ω , RV lead)

The following document is required for the RA lead, RV lead, and LV lead measurements:

- Print a copy of the Quick Notes Report from the PRM.

Lead measurement testing is required unless a rationale is provided. For example, the measurement is prohibited by a subject's condition.

It is recommended that the PCT measurements be collected in the following fashion:

- At least 3 cardiac cycles at a given voltage level are obtained before stepping down to the next voltage level.
- A count of two non-capture beats at a given voltage level is reached before declaring a loss of capture (LOC) for any of these tests.

It is recommended that the threshold be defined as one voltage level above the level where two non-captured beats are observed. If multiple PCT tests were performed, only the final measurement is required to be entered on the CRF.

11.5.9. LV VectorGuide Test

At the 6 Month Visit, the VectorGuide test should be performed prior to performing the SmartDelay test by selecting the VectorGuide test under the Test tab from the main programmer screen.

Responder Group

For subjects classified in the Responder Group, it is required that the RV-LV interval value be measured from all 4 electrodes as cathode (LVTip1, LVRing2, LVRing3, and LVRing4) by starting the LV VectorGuide test; however, it is not required to complete all steps of the LV VectorGuide test once the RV-LV intervals are collected. If the LV VectorGuide test is completed, also provide the number of viable pacing vectors.

Subjects must have RV and LV sensed beats for the test to be successful. If the subject does not tolerate a low intrinsic heart rate, stop the test and provide the rationale for not completing the required test (e.g. subject needs RV pacing support).

The following values are required to be collected in the Responder Group:

- Select the unipolar vectors and run the RV-LV Delay test for all 4 unipolar vectors to obtain RV-LV delay values.

The following values are required to be collected only if the LV VectorGuide test is completed:

- Number of viable pacing vectors (See definition in **Section 8.2**)

The following document is required in the Responder Group:

- Print a copy of the LV VectorGuide Report from the PRM.

Non-Responder Group

For subjects classified in the Non-Responder Group, it is required to use the LV VectorGuide to assess viable LV pacing vectors from all 17 pacing vectors.

For all 17 pacing vectors, the following values are required to be collected for subjects in the Non-Responder Group:

- RV-LV delay
- LV pacing impedance
- PNS test results
- LV Quick Capture threshold test
- Number of viable pacing vectors (See definition in **Section 8.2**)

The following document is required for subjects in the Non-Responder Group:

- Print a copy of the LV VectorGuide Report from the PRM.

For subjects classified in the Non-Responder Group, the LV pacing vectors will be recommended by the required SmartVector test; however, since it is not required to follow

the recommendation from the SmartVector, final pacing vectors are per the investigator discretion.

LV MSP Status in Non-Responder Group

Subjects who have at least 2 viable pacing vectors identified using the LV VectorGuide test or determined by the investigator will have the LV MSP feature turned on.

Subjects who do not have at least 2 viable pacing vectors identified will continue to be followed in the study but will not have the LV MSP feature turned on due to lacking of 2 viable pacing vectors.

11.5.10. RVp-LVs Interval Test

The data collected in this section will be used for future product feature enhancement or development, and are not associated with the primary and ancillary objectives. A deviation is not required if the test is not performed or the ECG/EGM strips are not sent to BSC.

Set the EGM channels to RA, RV and LV, pacing mode to VVI, LRL to 10 to 15 beats above the subject's intrinsic rate and ventricular pacing chamber to RV Only. Obtain the ECG/EGM strips at the paper speed of 100 mm/s for approximately 3-5 representative beats in two LV sense vector configurations: LVTip1 to Can and LVRing2 to Can, respectively. Record the Subject ID, visit information (Enrollment, 6 Month, or 12 Month), and the cathode of the LV sensing configuration (LVTip1 or LVRing2) on each ECG/EGM strip. Copies of all ECG/EGM strip should be submitted to BSC quarterly or more frequently, and before study ends.

11.5.11. SmartDelay Test

It is required to perform the SmartDelay test for all subjects to obtain programming recommendations for the AV Delay and Pacing Chamber. It is per the investigator discretion whether to follow the programming recommendations. However, the Pacing Chamber that is selected for a subject at the Enrollment Visit must be used for that subject through the 6 Month Visit (all subjects) or through the 12 Month Visits (for non-responders). For subjects in the Responder Group, there is no requirement to keep the same Pacing Chamber as these subjects are completing the study at the end of the 6 Month Visit.

The LV offset is required to be set at 0 ms prior to running the SmartDelay test. For non-responders, it is recommended that the LV pacing vector is set to a viable vector (from the LV VectorGuide test) with the longest RV-LV delay before running the SmartDelay test.

The SmartDelay test nominal Temporary Paced Lower Rate Limit (LRL) is set at 80 bpm. It is recommended to set the LRL at 10 to 15 bpm above the subject's intrinsic heart rate before conducting the SmartDelay test.

The following values from the SmartDelay test are required to be collected:

- SAV and PAV, both the recommended and final programmed values.
- Pacing Chamber (BiV or LV Only), both the recommended and final programmed values.

- Rationale if the SmartDelay recommendations are not followed.

The following documents from the SmartDelay test are required:

- Set EGM channels to RA, RV, and LV. Obtain ECG/EGM strips at the paper speed of 100 mm/s for approximately 3-5 representative beats during the Atrial Sense test and Atrial Pace test, respectively. The following values are required to be measured from the ECG/EGM strips:
 - Asense-RVsense, Asense-LVsense, Apace-RVsense, and Apace-LVsense intervals for each of the representative beats
 - Calculate the mean value for each of the 4 intervals from these representative beats

Record the Subject ID and visit information (Enrollment, 6 Month, or 12 Month) on each ECG/EGM strip. Copies of all ECG/EGM strip should be submitted to BSC quarterly or more frequently, and before study ends. The data collected in this test will be used for future product feature enhancement or development, and are not associated with the primary and ancillary objectives. A deviation is not required if the ECG/EGM strips are not sent to BSC.

- Print a copy of the Settings Changes Report from the PRM immediately after running the SmartDelay test and before any other setting changes are made and programmed. This report will display the recommended changes to the SAV, PAV, and Pacing Chamber at pending status.

If the SmartDelay test fails to complete, re-perform the test to obtain the recommended value. If the SmartDelay test was complete but not successful, the recommended value will be the nominal value used by SmartDelay. The SmartDelay test should be limited to two attempts in total.

11.5.12. SmartVector Operation (Non-Responders with LV MSP on)

For subjects who will receive the LV MSP therapy, it is required to use SmartVector to obtain recommendations for LVa and LVb pacing vectors after performing the LV VectorGuide tests. It is recommended to use the pacing vectors recommended by the SmartVector test; however, final selection of the 2 pacing vectors is per investigator discretion.

The following values are required to be collected for subjects who have the LV MSP turned on:

- The pacing configuration of LVa and LVb, both the recommended and final programmed vectors.
- Rationale if the SmartVector recommendations are not followed.

The following document is required for subjects who have the LV MSP on:

- Print a copy of the Settings Changes Report from the PRM before setting changes are made and programmed to show the recommended changes to the LVa and LVb vectors.

11.5.13. SmartOffset Operation (Non-Responders with LV MSP on)

For subjects who will receive the LV MSP therapy, it is required to use SmartOffset to obtain recommendations for the offset value between LVa, LVb, and RV. It is recommended to use the offset provided by the SmartVector operation; however, the final programmed offset is per investigator's discretion.

The following values are required to be collected for Non-Responders with the LV MSP turned on:

- Offset from LVa to LVb to RV, both recommended and final programmed.
- Offset from LVa to LVb if LV only pacing is programmed, both recommended and final programmed.
- Rationale if the SmartOffset recommendations are not followed.

The following document is required to be collected for Non-Responders with the LV MSP turned on:

- Print a copy of the Settings Changes Report from the PRM before setting changes are made and programmed to show the recommended changes to the offset.

11.5.14. LV MSP Settings Programming

Complete the programming of the LV MSP settings for subjects in the Non-Responder Group who have the LV MSP on. It is required that the LV MSP feature be turned on from the 6 Month Visit to the 12 Month Visit. The investigator may consider turning off the LV MSP feature if a subject experiences worsening symptoms. The subject may continue to receive conventional CRT. A rationale and study deviation are required if the LV MSP feature is turned off.

11.5.15. Battery Consumption

The following values are required to be collected:

- Time to explant
- Charge Remaining

11.5.16. Final device settings and status

Print a copy of the Device Settings Report from the PRM for all subjects at the 6 Month Visit and clear the device counters as the final step. For non-responder subjects with at least 2 viable LV pacing vectors, it is required to turn on the LV MSP feature. The pacing chamber (BiV or LV only) is required to be the same as determined at the Enrollment Visit. All other programming settings are per investigator discretion.

11.5.17. Adverse Event Assessment

Study required adverse event data will be collected and assessed for each subject. Hospitalization records are required to be sent to BSC. See **Section 20** for Adverse Event collection and reporting requirements.

11.5.18. HeartLogic Alert

The HeartLogic Alert feature is newly available in the Resonate family of devices. If the HeartLogic Alert feature is turned on, then the HeartLogic Alert(s) that resulted in a change in the subject's medical treatment will be collected.

11.5.19. "Save All" Device Data

Device data is required to be downloaded on a USB disk using "Save All" method if the subject is not enrolled in the LATITUDE Remote Monitoring System. Downloading the data requires ending the PRM session with the device. Hence, it is recommended to complete all other study activities that require PRM-device communication prior to this step. For subjects enrolled in the LATITUDE Remote Monitoring System, device data will be transmitted to BSC automatically on a regular basis and do not require manual download.

The original USB disk will be retained at the site and a copy of the disk should be submitted to BSC quarterly or more frequently. Label the Subject ID and visit information (6 Month or 12 Month) on both USB disks. The data collected in this section will be used for future product feature enhancement or development, and are not associated with the primary and ancillary objectives. A deviation is not required if the "Save All" USB disk is not performed or submitted to BSC.

A summary of the source documentation required at the 6 Month Visit is described in **Table 11.5-2**.

Table 11.5-2: Source Documentation Requirement at the 6 Month Visit

Source Documentation Requirement	Disposition
NYHA class assessment	Retain at study site
Patient Global Assessment	
Physician Global Assessment	
Adverse event assessment	
Device Settings Report, Settings Changes Report, Quick Notes Report, LV VectorGuide Report	
Hospitalization record	
Echo measurement, if performed per standard of care	
Manually recorded Charge Remaining	

Source Documentation Requirement	Disposition
ECG/EGM Strips from the SmartDelay test	Retain at study site Submit 1 copy to BSC
ECG/EGM Strips from the RVp-LVs interval test	
“Save All” device data on USB disk, if applicable	

11.6. 12 Month Visit

The 12 Month Visit must be performed in office at 183 -0 day/+30 days post-6 Month Visit for subjects who were classified in the Non-Responder Group at the 6 Month Visit. A list of the data to be collected at the 12 Month Visit is provided below, with further details included in the sections below.

- NYHA class assessment
- Patient Global Assessment
- Physician Global Assessment
- HF Event
- Response status determination
- Echo measurement
- Current device setting and status
- Lead measurements
- SmartDelay test and value
- Asense to Vsense and Apace to Vsense intervals
- LV VectorGuide test and value
- RVp-LVs interval test
- SmartVector and SmartOffset value
- Battery consumption
- Final device settings and status
- Adverse event assessment
- HeartLogic Alert
- “Save All” device data

11.6.1. Definition and Components of the Clinical Composite Score

The CCS will be calculated for all subjects at the 12 Month Visit. The CCS consists of the following components:

- All-cause mortality
- Heart Failure (HF) event
- Patient Global Assessment (PGA)
- NYHA class

11.6.1.1. HF Event Definition

For the purpose of the CCS calculation, HF event is defined as an adverse event with a primary cause of HF and either of the conditions below is met:

- Subject is admitted and discharged with a calendar date change.
- Subject is not hospitalized but received one or more IV medications including diuretics, inotropes, vasodilators, other parenteral therapy, or aquapheresis.

11.6.1.2. PGA Classification

Interpretation of no change status in PGA is defined as the following:

- A little better, no change, and a little worse.

Per CCS definition, a little better and a little worse are considered as placebo effect and are treated as no change.

The investigator will use the subject's response to the PGA and classify response of "a little better", "no change", or "a little worse" to the category of "no change". Subsequently, the investigator will use "very much better", "much better", "no change", "much worse", and "very much worse" to determine the status of PGA changes.

11.6.1.3. NYHA Class Assessment

See Section 11.4.4 for a detailed description of performing NYHA Class assessment.

11.6.1.4. CCS Status Classification

Subjects will be classified as improved, unchanged, or worsened by comparing their clinical response in the current visit to their last visit. At the 12 Month Visit, subjects' status will be compared to their status at the 6 Month Visit. The following criteria will be used:

- Improved: Subjects are considered improved if they experienced a favorable change in at least one NYHA functional class or in the PGA (or both) while remaining alive and free of HF event comparing to their status in the 6 Month Visit. See **Table 11.5-1** on selecting improved PGA status.
- Worsened: Subjects are considered worsened if any of the followings occurs:
 - died (from any cause) or
 - experienced a HF event or
 - reported worsening of at least one NYHA functional class or

- reported worsening of the PGA comparing to their status in the 6 Month Visit. See **Table 11.5-1** on selecting worsened PGA status.
- Unchanged: Subjects are considered unchanged if they are neither improved nor worsened.

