8.3. Justification for the Study Design

This study is designed to evaluate the therapy benefit provided by multisite pacing to those patients who are non-responders to CRT with single site LV pacing based on a clinical evaluation using the CCS. The study's primary endpoint of the Clinical Composite Endpoint (CCS) measures multiple components related to the improvement of patient's clinical status, including Patient Global Assessment, NYHA class change, heart failure event, and mortality rate. See **Section 11.5.1** for the definition and calculation used in the study. These measures are well-understood and widely accepted by the medical community.

9. Subject Selection

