11.5.1.4. CCS Status Classification

Subjects will be classified as improved, unchanged, or worsened by comparing their clinical response in the current visit to their last visit. At the 6 Month Visit, subjects' status will be compared to their status immediately prior to receiving the CRT-D implantation. The following criteria will be used:

- Improved: Subjects are considered improved if they experienced a favorable change in at least one NYHA functional class or in the PGA (or both) while remaining alive and free of HF event comparing to their status in the Enrollment Visit. See **Table 11.5-1** on selecting improved PGA status.
- Worsened: Subjects are considered worsened if any of the followings occurs:
 - died (from any cause) or
 - experienced an HF event or
 - reported worsening of at least one NYHA functional class or
 - reported worsening of the PGA comparing to their status immediately prior to receiving the CRT-D implantation. See **Table 11.5-1** on selecting worsened PGA status.
- Unchanged: Subjects are considered unchanged if they are neither improved nor worsened.

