12.1.2. Primary Effectiveness Endpoints: Proportion of LV MSP Group with an Improved CCS

The effectiveness endpoint for SMART MSP PAS is the proportion of the LV MSP Group with an Improved CCS. Details regarding the CCS are provided in **Section 11.5.1**. For this endpoint, those subjects in the LV MSP Group that become responders will be defined as having an Improved CCS as discussed in **Section 11.5.1**. This endpoint will be evaluated at the 12 Month Visit to determine if the LV MSP Group subjects improved from their 6 Month Visit.

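### The CCS categories Improved and Worsened overlap when NYHA class and PGA move in opposite directions, so the 12-month primary effectiveness outcome is contradictory for such a subject

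*Combined protocol and SAP*

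**What the plan says.** Section 11.6.1.4 sets three categories at the 12 Month Visit.

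- **Improved.** "Improved: Subjects are considered improved if they experienced a favorable change in at least one NYHA functional class or in the PGA (or both"), with one attached condition: "while remaining alive and free of HF event comparing to their status in the 6 Month Visit".
- **Worsened.** Any single item is enough: death, an HF event, a loss of at least one NYHA class, or "reported worsening of the PGA comparing to their status in the 6 Month Visit".
- **Unchanged.** "Subjects are considered unchanged if they are neither improved nor worsened".

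Section 11.6.1.2 counts a PGA answer as a change only if it is much or very much better or worse. Section 11.6.5 maps Improved to responder and Worsened or Unchanged to non-responder.

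Section 12.1.2 says that LV MSP Group subjects who become responders "will be defined as having an Improved CCS as discussed in" Section 11.5.1, which is the 6 Month Visit section. It also says that the endpoint is assessed at 12 months "to determine if the LV MSP Group subjects improved from their 6 Month Visit". Section 8.3 likewise sends the reader to 11.5.1 "for the definition and calculation used in the study". In 11.5.1.4, status at the 6 Month Visit "will be compared to their status immediately prior to receiving the CRT-D implantation", although its Improved bullet names the Enrollment Visit.

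**The concern.** Only death and an HF event bar a subject from Improved. Deterioration in the other symptom measure does not, yet that deterioration alone makes the subject Worsened. The residual category cannot absorb the case, because such a subject meets both definitions rather than neither.

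The primary endpoint is the proportion Improved, tested against 5%. As written, a discordant subject belongs both in that numerator and in the Worsened percentage of Section 12.2.3. Discordance is plausible, because two people supply the inputs: blinded site staff assess NYHA class (11.6.2) and the subject completes the PGA (11.6.3). The investigator or delegated staff then assign the label (11.6.5), so sites could resolve identical cases differently.

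The cross-reference adds a second difficulty. Repairing 11.6.1.4 alone would leave the endpoint section pointing to an unrepaired definition with a different reference time. At 6 months the same overlap affects the responder label. That label, together with having at least two viable vectors (11.5.9), helps decide who has LV MSP turned on.

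**Working it through.** **1. Applying the written rules**

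For subjects alive and free of an HF event:

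| NYHA class | PGA better | PGA no change | PGA worse |
|---|---|---|---|
| Better | Improved | Improved | **Improved and Worsened** |
| Same | Improved | Unchanged | Worsened |
| Worse | **Improved and Worsened** | Worsened | Worsened |

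Two of nine cells carry both labels. With death or an HF event, all nine combinations are Worsened, so 2 of 18 collide in total. This counts rule conflicts; it is not a frequency.

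**2. Searching for a precedence rule**

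None appears in 11.5.5, 11.6.5, 12.1.2, 12.1.2.3, 12.2.3 or Table 25.2-1. The Clinical Events Committee's role in the CCS is to adjudicate HF events (12.4.3, 22.2); it is given no role in NYHA–PGA disagreements.

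**3. The plan's own sample size**

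Inputs from 12.1.2.2: n = 110, performance goal 5%, expected rate 15%, one-sided 5% exact binomial test, power 95%.

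- Cut-off: the smallest r with P(X ≥ r | 110, 0.05) ≤ 0.05. P(X ≥ 9) = 0.1002 and P(X ≥ 10) = 0.0492, so r = 10.
- Check by the exact lower 95% limit (the 0.05 quantile of Beta(x, 110 − x + 1)): 9/110 gives 4.33% and fails; 10/110 gives 5.02% and passes.
- Power: P(X ≥ 10 | 110, 0.15) = 0.9756, so 110 subjects more than meet the stated 95%.

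One discordant subject can decide the result at the boundary between 9 and 10.

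**4. Size of the effect**

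The discordant share d is an assumption; the documents give none. Suppose the planned 15% includes d. Scoring discordant subjects Worsened gives power P(X ≥ 10 | 110, 0.15 − d).

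| Assumed d | Expected discordant (110 × d) | Rate if scored Worsened | Power | Loss from 97.56% |
|---|---|---|---|---|
| 0.5% | 0.55 | 14.5% | 96.65% | 0.91 points |
| 1% | 1.1 | 14% | 95.45% | 2.11 points |
| 2% | 2.2 | 13% | 91.91% | 5.65 points |

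The last column is also the probability that the scoring choice changes the conclusion: clear Improved below 10, but clear plus discordant at least 10. It is one quantity read two ways.

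The choice matters more nearer the goal. If the total rate including discordant subjects were 9%, with d = 1%, the chance of passing would be 53.5% one way and 38.5% the other, a difference of 15.0 points. If clear improvement were exactly 5%, counting a further 1% of discordant subjects as Improved would raise the chance of passing from 4.9% to 12.5%.

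**5. The cross-reference**

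12.1.2 wants change from the 6 Month Visit. The section it cites compares with status before implant, or at enrollment in its Improved bullet. Neither is the 6 Month Visit. The section with the right reference time is 11.6.1.

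**The case against.** The strongest reply concerns weight. A collision needs a surviving subject without an HF event, a full NYHA class moved one way, and a PGA of much or very much the other way. Such subjects are probably few, and every rate above is assumed. At 0.5% and 1%, power still meets the stated 95%; only at 2% does it fall below. The loss also presupposes that the planned 15% counted discordant subjects as Improved, which 12.1.2.2 does not say. All of this stands, and it limits the size of the effect. It does not remove the contradiction.

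The cross-reference can fairly be called editorial. Section 12.1.2 itself states the 6-month comparison, and 11.6.1.4 gives the 12-month rule, so a careful reader would hardly use a pre-implant baseline. On its own this part is minor. It matters because 12.1.2 would still cite an overlapping definition after 11.6.1.4 was repaired.

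A third reply is that sites assign the label at the visit, before any pooled result is known, so the choice would not be made with the outcome in view. That is partly right, but it replaces one risk with another, namely inconsistent labels between sites. Section 12.1.2.3 lists the four components without saying how to combine them when they disagree.

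Finally, letting Worsened prevail is not the only exclusive scheme; discordant subjects could be called Unchanged. The primary result is the same either way, since both are non-responders under 11.6.5. Only the Worsened percentage in 12.2.3 differs.

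**Conclusion.** The concern holds. The rule for the primary effectiveness outcome gives two incompatible labels for a definable set of subjects, and nothing elsewhere in the documents settles which applies. This is an error in the rule as written, not just a missing detail.

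The likely effect is small. At the planned 15% response with n = 110, the choice of label would change the conclusion in about 0.9%, 2.1% or 5.7% of trials for assumed discordant shares of 0.5%, 1% or 2%. It would matter more if the true rate lay closer to 5%. These figures rest on the assumed shares and on the 15% including discordant subjects. The point should be fixed: the repair is cheap before the endpoint analysis, and a rule chosen with the results in view could not be neutral.

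**What to change.** **12-month primary endpoint**

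1. In 11.6.1.4, define Improved as a favourable change in NYHA class or PGA with no Worsened criterion met. This follows the any-one-item form of Worsened and is the conservative choice for the primary test.
2. In 12.1.2, change both references from 11.5.1 to 11.6.1, and add 11.6.1 to the pointer in 8.3.
3. Derive the category by program from the four recorded components, using adjudicated HF events.
4. Report the number of discordant subjects and repeat the primary test with them scored the other way.

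This label drives no in-study treatment: subjects complete the study at that visit, and later programming is left to the investigator (11.6.14).

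**6-month classification**

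The sponsor must reconcile the overlapping definitions in 11.5.1.4 and their use in 11.5.5. No rule is proposed here, because that label bears on device programming. If the two visits end up with different rules, 12.1.2 and Table 25.2-1 should say which applies when.

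**Cost**

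The 12-month change needs one sentence, corrected references and one derived variable; all four components are already collected (12.1.2.3). Section 12.5.5 allows analysis changes through a SAP approved beforehand. Because this clarifies a primary-endpoint category, an amendment with approvals may be needed under Section 14. The downside is that slightly fewer subjects may count as Improved. The 6-month wording needs a separate sponsor decision.
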